5. SUBJECT ENROLLMENT

Before subjects begin participation in any study-specific activities/procedures, Amgen requires a copy of the site's written institutional review board (IRB) approval of the protocol, informed consent form (ICF), and all other subject information and/or recruitment material, if applicable (see Section 11.2). All subjects must personally sign and date the consent form before commencement of study-specific procedures. SAEs, **ADEs**, and study-related AEs will be collected upon signing the informed consent form.

A subject is considered enrolled when the investigator decides that the subject has met all eligibility criteria assessed at screening. The investigator is to document this decision and date, in the subject's medical record and in/on the enrollment eCRF.

Each subject who enters into the screening period for the study (defined as signing the informed consent form) receives a unique subject identification number before any study-related activities/procedures are performed. The subject identification number will be assigned by interactive voice response system or interactive web response system (IVRS/IWRS). This number will be used to identify the subject throughout the clinical study and must be used on all study documentation related to that subject.

The subject identification number must remain constant throughout the entire clinical study; it must not be changed after initial assignment, including if a subject is rescreened.

5.1 Randomization/Treatment Assignment

Assignment to the 4 treatment arms (Section 3.1) will be based on a computer-generated randomization schedule prepared by Amgen before the start of the study.

Each subject will receive a unique randomization number. Randomization will be stratified by entry statin therapy (no statin use vs non-intensive statin use vs intensive statin use [see Appendix D] and by the site's geographic region.

Once a subject has completed the end of lipid stabilization assessments and continues to meet all eligibility criteria, a site representative will make the randomization call to the IVRS/IWRS to assign a randomization number to the subject. The randomization call to the IVRS/IWRS is accomplished by entering the pertinent information detailed in the IVRS/IWRS user manual. A confirmation fax or email will be sent to the site to verify that

the correct information has been entered and to confirm the assignment of a randomization number. A subject will be considered randomized into the study when a randomization number is assigned.

The randomization date is to be documented in the subject's medical record and on the enrollment eCRF.

5.2 Site Personnel Access to Individual Treatment Assignments

A subject's treatment assignment should only be unblinded when knowledge of the treatment is essential for the further management of the subject on this study. Unblinding at the study site for any other reason will be considered a protocol deviation. The investigator is strongly encouraged to contact the Clinical Study Manager before unblinding any subject's treatment assignment, but must do so within 1 working day after the event.

6. TREATMENT PROCEDURES

6.1 Classification of Products and/or Medical Devices

The Amgen investigational products used in this study include: evolocumab and matching placebo.

The non-Amgen non-investigational products used in this study include: atorvastatin 20 mg.

The Investigational Product Instruction Manual (IPIM), a document external to this protocol, contains detailed information regarding the storage, preparation, **destruction**, and administration of evolocumab, matching placebo, and atorvastatin.

The medical devices used in this study include: prefilled autoinjector/pen and 3.5 mL Personal Injector.

6.2 Investigational Product

6.2.1 Evolocumab (Amgen Investigational Product)

Evolocumab and placebo will be manufactured and packaged by Amgen Inc. and distributed using Amgen clinical IP distribution procedures. Evolocumab and placebo SC will be provided in 2 different injection devices:

- A single use, disposable, handheld mechanical (spring-based) prefilled autoinjector/pen (AI/Pen) for fixed dose, subcutaneous injection of 140 mg evolocumab in 1.0 mL deliverable volume or an identical volume of placebo. The AI/Pen is intended for Q2W administration.
- A single-use, disposable, on-body electro-mechanical 3.5 mL Personal Injector that is co-packaged with a prefilled Crystal Zenith[®] (CZ) cartridge assembly for

fixed dose, subcutaneous injection of 420 mg evolocumab in 3.5 mL deliverable volume or an identical volume of placebo. The 3.5 mL Personal Injector is intended for QM administration. If the 3.5 mL Personal Injector is unavailable, QM dosing may be provided by 3 injections by AI/Pen.

The prefilled Al/Pen contains a 1.0 mL deliverable volume of 140 mg/mL evolocumab in **CCI** mM proline, **CC** mM acetate, **CCI**% (weight/volume [w/v]) polysorbate 80, pH **CCI** or, for placebo, a 1.0 mL deliverable volume of **CC**% (w/v) sodium carboxymethylcellulose, **CCI** mM proline, **CCI** mM acetate, and **CCI**% (w/v) polysorbate 80, pH **CC**.

The prefilled Crystal Zenith[®] (CZ) cartridge assembly of the Personal Injector contains a 3.5 mL deliverable volume of 120 mg/mL evolocumab in \bigcirc mM proline, \bigcirc mM acetate, \bigcirc (w/v) polysorbate 80, pH \bigcirc or, for placebo, a 3.5 mL deliverable volume of \bigcirc (w/v) sodium carboxymethylcellulose, \bigcirc mM proline, \bigcirc mM acetate, and \bigcirc (w/v) polysorbate 80, pH \bigcirc .

Evolocumab and placebo should be stored refrigerated and protected from light according to the storage and expiration information provided on the label (where required).

Al/Pen and 3.5 mL Personal Injector should be inspected for IP quality, expiry, and damage before using per the instructions provided in the IPIM. Damaged, expired, or degraded product should not be used and any issues with the prefilled Al/Pen or 3.5 mL Personal Injector should be reported to Amgen.

Further details are provided in Section 6.7, in the IPIM and the respective Instructions for Use (IFU) for the devices.

6.2.1.1 Dosage, Administration, and Schedule

Subcutaneous IP (evolocumab or matching placebo) will be administered SC in accordance with instructions in the IPIM. IP administration by SC injection if performed during a study visit must occur after vital signs, electrocardiogram (ECG), and blood draw procedures, if applicable. After IP administration at the first dosing visit, subjects will be held for observation for at least 30 minutes before being discharged.

IP will be administered at either 140 mg evolocumab or placebo in 1.0 mL (administration by prefilled AI/Pen) Q2W or 420 mg evolocumab or placebo in 3.5 mL (administration by 3.5 mL Personal Injector) QM.

In this study, subjects have the option of self-administration, defined as SC administration of IP by the subject, designee or a qualified health care professional in a

non-investigator site setting (eg, at home). The subject (or designee, if not a qualified healthcare professional) must have demonstrated competency at administration of SC injections before self-administration is permitted: the first self-administered dose by the subject (or designee, if not a healthcare professional) must be administered at the site under the supervision of a healthcare provider.

Details of preparing IP and the injection procedures are included in the IPIM provided by Amgen prior to the start of the study. The dosing schedule is described by a schema in the protocol synopsis.

When IP is mandated to be administered at the study site, the date and completion time of administration, the body location of the injection, and whether the injection was fully or partially administered are to be recorded on each subject's CRF.

When IP can be administered at a non-investigator site location, at a minimum, the dates the devices were dispensed and the used devices returned, and for each device whether it was returned fully or partially used are to be recorded on each subject's CRF.

6.2.1.2 Dosage Adjustments, Delays, Rules for Withholding or Restarting, Permanent Discontinuation

There will be no dose adjustments in this study. If, in the opinion of the investigator, a subject is unable to tolerate a specific dose of IP, that subject will discontinue IP but will continue to take atorvastatin and return for all other study procedures and measurements until the end of the study.

If a subject is late for administration of IP, administration should occur as soon as possible. A QM dose of IP should not be administered within less than 7 days of a previous dose. If a QM subject arrives for a visit with IP administration and IP was administered within the prior 7 days, the dose should not be administered but all other study procedures should be conducted. Administration of IP should occur as soon as possible but at least 7 days after the previous administration. Not more than 2 Q2W doses should be administered within any 7-day period. If a Q2W subject arrives for a visit with IP administration and more than 1 dose of IP was administered within the prior 7 days, the dose should not be administered but all other study procedures should be administered but all other a visit with IP administration and more than 1 dose of IP was administered within the prior 7 days, the dose should not be administered but all other study procedures should be completed. Administration of IP should occur as soon as possible but at least 7 days after the most recent previous administration.

Subjects who completely miss a dose of IP will continue in the study and receive the next dose of IP per their schedule of administration.

6.2.2 Atorvastatin (Non-Amgen Non-investigational Product)

Atorvastatin (non-Amgen non-investigational product) will be used in this study as background therapy. Atorvastatin will be provided by Amgen. Additional details regarding this product are provided in the Investigational Product Instruction Manual (IPIM).

6.2.2.1 Dosage, Administration, and Schedule

Atorvastatin 20 mg will be taken orally once daily and should be taken every day at about the same time in accordance with instructions in the IPIM. If taken during a study visit, it must be taken after vital signs, ECG, and blood draw procedures have been completed, if applicable.

The start date of atorvastatin administration, the dates atorvastatin is dispensed and the used containers returned, and the quantity returned are to be recorded on each subject's CRF.

6.2.2.2 Dosage Adjustments, Delays, Rules for Withholding or Restarting, Permanent Discontinuation

There will be no dose adjustments for atorvastatin in this study. If, in the opinion of the investigator, a subject is unable to tolerate a specific dose of atorvastatin after having been randomized to IP, the Amgen medical monitor should be contacted. If atorvastatin is discontinued, IP (evolocumab or matching placebo) should be continued unless there is a reason to discontinue IP as well. In either case, the subject should return for all other study procedures and measurements until the end of the study.

Subjects who miss a dose of atorvastatin will be advised to take the missed dose as soon as they can; subsequent doses will be taken at the usual time. However, if the next scheduled dose would be due in less than 6 hours, the subject will be advised to omit the missed dose entirely and to take the next dose at the normal time.

6.3 Non-investigational Products

All other lipid-lowering drugs that are allowed per protocol and that the subject may be taking, must be commercially available and are not provided or reimbursed by Amgen (except if required by local regulation). The investigator will be responsible for obtaining supplies of these drugs. All such therapy needs to be stable and unchanged during the entire time of screening and study participation.

6.4 Withholding of Investigational Product or Atorvastatin due to Elevation of Creatine Kinase (CK)

If CK is > 5x ULN, CK must be retested before atorvastatin and IP is administered. In addition, investigators will ask study subjects to promptly report muscle pain, cramps, or weakness especially if accompanied by malaise or fever. If such symptoms occur, the subject's CK levels should be measured and if CK is > 5x ULN, the subject should be instructed to discontinue atorvastatin and IP. CK must be retested before any atorvastatin or IP is administered.

The following rules apply:

CK at prior visit	CK on retest	Investigational Product Administration
> 5x ULN	> 10x ULN	Discontinue atorvastatin and IP ^a . Contact Amgen Medical Monitor
	> 5x to ≤ 10x ULN	Discontinue atorvastatin and retest CK before atorvastatin administration. Consider continuing IP if alternative explanation
	≤ 5x ULN	Consider continuing IP and atorvastatin

^a CK elevations >10x ULN that have been confirmed to be secondary to myocardial infarction do not require discontinuation of IP or atorvastatin

If muscular symptoms are severe and cause daily discomfort, even if the CK levels are elevated to $\leq 5x$ ULN, in consultation with the Amgen medical monitor, discontinuation of atorvastatin, or introduction of an alternative statin may be considered at the lowest dose and with close monitoring. Please note that Amgen will not be providing the alternative statin.

6.5 Hepatotoxicity Stopping and Rechallenge Rules

Subjects with abnormal hepatic laboratory values (ie, alkaline phosphatase [ALP], aspartate aminotransferase [AST], alanine aminotransferase [ALT], total bilirubin [TBL]) and/or international normalized ratio [INR] and/or signs/symptoms of hepatitis (as described below) may meet the criteria for withholding or permanent discontinuation of Amgen investigational product or other protocol-required therapies as specified in the Guidance for Industry Drug-Induced Liver Injury: Premarketing Clinical Evaluation, July 2009).

6.5.1 Criteria for Permanent Discontinuation of Amgen Investigational Product and Other Protocol-required Therapies due to Potential Hepatotoxicity

Atorvastatin and investigational product should be discontinued permanently and the subject should be followed according to the recommendations in Appendix A (Additional

Safety Assessment Information) for possible drug-induced liver injury (DILI), if ALL of the criteria below are met:

• TBL > 2x ULN or INR > 1.5 (testing determined per Appendix A)

AND

• AST or ALT > 3x ULN

AND

- no other cause for the combination of the above laboratory abnormalities is immediately apparent; important alternative causes for elevated AST/ALT and/or TBL values include, but are not limited to:
 - hepatobiliary tract disease
 - viral hepatitis (eg, hepatitis A/B/C/D/E, Epstein-Barr virus, cytomegalovirus, herpes simplex virus, varicella, toxoplasmosis, and parvovirus)
 - right sided heart failure, hypotension or any cause of hypoxia to the liver causing ischemia.
 - exposure to hepatotoxic agents/drugs or hepatotoxins, including herbal and dietary supplements, plants and mushrooms
 - heritable disorders causing impaired glucuronidation (eg, Gilbert's Syndrome, Crigler-Najjar syndrome) and drugs that inhibit bilirubin glucuronidation (eg, indinavir, atazanavir)
 - alpha-one antitrypsin deficiency
 - alcoholic hepatitis
 - autoimmune hepatitis
 - Wilson's disease and hemochromatosis
 - nonalcoholic fatty liver disease including steatohepatitis (NASH)
 - Non-hepatic causes (eg, rhabdomyolysis, hemolysis)

6.5.2 Criteria for Conditional Withholding of Amgen Investigational Product and Other Protocol-required Therapies due to Potential Hepatotoxicity

For subjects who do not meet the criteria for permanent discontinuation of Amgen investigational product outlined above and have no underlying liver disease, and eligibility criteria requiring normal transaminases and TBL at baseline or subjects with underlying liver disease and baseline abnormal transaminases, the following rules are to be followed for withholding of Amgen investigational product and other protocol-required therapies:

- AST or ALT > 8x ULN at any time
- AST or ALT > 5x ULN but < 8x ULN for ≥ 2 weeks (or subject unable to adhere to enhanced monitoring schedule)

- ALT or AST > 3x ULN with clinical signs or symptoms that are, in the opinion of the investigator, consistent with hepatitis (such as right upper quadrant pain/tenderness, fever, nausea, vomiting, jaundice, rash or eosinophilia > 5%)
- TBL > 3x ULN at any time
- ALP > 8x ULN at any time

Both atorvastatin and investigational product should be withheld pending investigation into alternative causes of DILI. If atorvastatin or investigational product is withheld, the subject is to be followed according to recommendations in Appendix A for possible DILI. Rechallenge may be considered if an alternative cause for impaired liver tests (ALT, AST, ALP) and/or elevated TBL, is discovered and the laboratory abnormalities resolve to normal or baseline (Section 6.5.3).

6.5.3 Criteria for Rechallenge of Amgen Investigational Product and Other Protocol-required Therapies After Potential Hepatotoxicity

The decision to rechallenge the subject should be discussed and agreed upon unanimously by the subject, investigator, and Amgen.

If signs or symptoms recur with rechallenge, then investigational product should be permanently discontinued. Subjects who clearly meet the criteria for permanent discontinuation (as described in Section 6.5.1) should never be rechallenged.

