Procedures: Subjects who have signed informed consent will undergo screening procedures including laboratory assessments and a 1-time administration of placebo by Al/Pen and will enter a lipid stabilization period where they will receive 20 mg atorvastatin daily (QD). Subjects should maintain their diet, any allowed therapy, and exercise regimen throughout screening and study participation. Eligible subjects will be scheduled to return to the study site after \geq 4 weeks of lipid stabilization to initiate IP administration and other day 1 procedures. For randomization, the site

will contact the interactive voice response system or interactive web response system (IVRS/IWRS). Day 1 is defined as the day of first administration of IP and should occur as close as possible or on the day of randomization but not later than 5 days after randomization. Subsequent mandatory study visits are at weeks 2, 8, 10, and 12 (EOS for QM subjects). In addition, subjects receiving IP Q2W will be contacted (eg, by phone call) by the study site at week 14 (EOS for Q2W subjects) to obtain AE, ADE, and SAE information, if applicable. For subjects randomized to receive IP Q2W, IP will be administered by AI/Pen at the study site on day 1, and weeks 2, 8, and 10. For subjects randomized to receive IP QM, IP will be administered by 3.5 mL Personal Injector at the study site on day 1, and week 8. For other administrations of IP by AI/Pen or 3.5 mL Personal Injector, respectively, subjects will have the option of self-administration, defined as SC administration of IP by the subject, designee or a qualified health care professional in a non-investigator site setting (eg, at home). The subject (or designee, if not a qualified healthcare professional) must have demonstrated competency at administration of SC injections before self-administration is permitted: the first self-administered dose by the subject (or designee, if not a healthcare professional) must be administered at the site under the supervision of a healthcare provider. Final administration of IP (evolocumab or placebo) is at week 8 for QM treatment and week 10 for Q2W treatment. Subjects who discontinue IP for any reason will be asked to continue to return for all other study procedures and measurements until the end of the study.

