- 210 Treatment in the last 2 months prior to screening and lipid stabilization assessments with any of the following drugs: systemic cyclosporine, systemic steroids (eg, intravenous [IV], intramuscular [IM], or oral [PO] administration), vitamin A derivatives and retinol derivatives for the treatment of dermatologic conditions (eg, Accutane); (Note: vitamin A in a multivitamin preparation is permitted).
- 211 Hyperthyroidism or hypothyroidism as defined by thyroid stimulating hormone (TSH) below the lower limit of normal (LLN) or > 1.5 times the upper limit of normal (ULN), respectively, at screening.
- 212 Moderate to severe renal dysfunction, defined as an estimated glomerular filtration rate (eGFR) < 30 mL/min/1.73m² at screening.
- 213 Persistent active liver disease or hepatic dysfunction, defined as aspartate aminotransferase (AST) or alanine aminotransferase (ALT) > 2 times the ULN as determined by central laboratory analysis at screening or lipid stabilization assessments.
- 214 Creatine kinase (CK) > 3 times the ULN at screening or lipid stabilization assessments.
- 215 Known active infection or major hematologic, renal, metabolic, gastrointestinal or endocrine dysfunction (except diabetes).
- 216 Deep vein thrombosis or pulmonary embolism within 3 months prior to randomization.
- 217 Female subject who has either (1) not used (an) acceptable method(s) of effective birth control (see below) for at least 1 month prior to screening and (2) is not willing to inform her partner of her participation in this clinical study and to use such (an) acceptable method(s) of effective birth control during treatment with IP (evolocumab or placebo) and for an additional 15 weeks after the end of treatment with IP (evolocumab or placebo), unless the female subject is permanently sterilized or postmenopausal (see below);

- A female is considered of childbearing potential unless **permanently** sterilized or postmenopausal with menopause defined as:
 - 12 months of spontaneous and continuous amenorrhea in a female
 ≥ 55 years old, or
 - 12 months of spontaneous and continuous amenorrhea with a follicle-stimulating hormone (FSH) level > 40 IU/L (or according to the definition of "postmenopausal range" for the laboratory involved) in a female < 55 years old
 - unless the subject has undergone bilateral oophorectomy

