7. STUDY PROCEDURES

7.1 Schedule of Assessments

	Screen & Lipid Stabilization			Treatment Period							Phone
Study Day / Week / Other Timepoint ^a	Screen	Enroll Start Atorva	End of Lipid Stabil	D1 Visit Rand.	W2 Visit	W4	W6	W8 Visit	W10 Visit	W12 Visit (QM EOS)	W14 ^b Q2W EOS
General Procedures											
Informed consent	Х										
Medical history	Х										
Vital Signs (sitting BP, HR)	Х			Х	Х				Х	Х	
Review for AEs/ADEs/SAEs	Xc		Xc	Х	Х	(X) ^d	(X) ^d	Х	Х	Х	Х
Concomitant therapy	Х		Х	Х	Х			Х	Х	Х	
Dietary instruction	Х			Х	Х			Х	Х		
Physical exam	Х									Х	
Body weight, waist circumference				Х						Х	
Body height	Х										
12 lead ECG	Х			Х					Х	Х	
Randomization				Xe							
Central Laboratory											
Fasting lipids ^g	Х		Х	Х	Х			Х	Х	Х	
ApoA1, ApoB100, Lp(a)				Х					Х	Х	
PK (evolocumab), PCSK9				Х	Х			Х	Х	Х	
Chemistry, including fasting glucose ^g	Х		Х	Х				Х		Х	
Hematology	Х			Х				Х		Х	
hsCRP				Х						Х	
HbA1c	Х									Х	
TSH	Х										
MMTT: Plasma glucose, insulin, proinsulin, C-peptide, free fatty acids, glucagon, lipids, chylomicrons, ApoB48, IL-6, adiponectin, vitamin E, measured after $a \ge 9$ hour fast just prior to a standardized meal (0 minutes), and then 120 minutes after ^h				Х						x	
MMTT Extended Timepoints Substudy: Same analytes as for MMTT, measured at additional timepoints (60, 180 minutes) in subjects participating in the substudy) ^h				Х						X	
Biomarkers (blood) ^{ji}				Х						Х	
Anti-evolocumab antibodies				Х						Х	
HCV testing ⁱ	Х										
HCV viral load ¹				X	Х			X		X	
Serum pregnancy; FSH ^k	Х		X							X	
Urine pregnancy				X	Х			Х			
Urinalysis, urine microalbumin				Х						Х	

Table 1. Schedule of Assessments

Footnotes defined on last page of this table.

Page 1 of 2

	Screen & Lipid Stabilization			Treatment Period							Phone
Study Day / Week / Other Timepoint ^a	Screen	Enrol Start Atorva	End of Lipid Stabil	D1 Visit Rand.	W2 Visit	W4	W6	W8 Visit	W10 Visit	W12 Visit (QM EOS)	W14 ^b Q2W EOS
Steroid analytes				Х						Х	
Investigational Product											
Screening placebo injection	Х										
Atorvastatin dispensation ^m	Х	Х	Х	Х	Х			Х			
Atorvastatin tablet count ^m	Х		Х	Х	Х			Х		Х	
Al/Pen / 3.5 mL Personal Injector Instruction	Х			Х	Х			Х			
Al/Pen / 3.5 mL Personal Injector dispensation					Х			Х			
Al/Pen / 3.5 mL Personal Injector reconciliation								Х			
Q2W IP on-site				Х	Х			Х	Х		
QM IP on-site				Х				Х			
Q2W IP on-site or in non-investigator site setting						Х	Х				

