8.2 Investigator or Sponsor Decision to Withdraw or Terminate Subject's Participation Prior to Study Completion

The investigator and/or sponsor can decide to withdraw a subject(s) from investigational product and/or other protocol-required therapies, protocol procedures, or the study as a whole at any time prior to study completion.

Subjects may be eligible for continued treatment with Amgen investigational product(s) and/or other protocol-required therapies by a separate protocol or as provided for by the local country's regulatory mechanism, based on parameters consistent with Section 12.1.

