14. APPENDICES

Appendix A. Additional Safety Assessment Information Adverse Event Grading Scale

Refer to the NCI Common Terminology Criteria for AEs (CTCAE) Version 4.0 for AE grading and information. The CTCAE is available at the following link: http://ctep.cancer.gov/protocolDevelopment/electronic_applications\ctc.htm.

Drug-induced Liver Injury Reporting & Additional Assessments

Reporting

To facilitate appropriate monitoring for signals of DILI, cases of concurrent AST or ALT and TBL and/or INR elevation according to the criteria specified in Section 6.4 require the following:

- The event is to be reported to Amgen as a serious adverse event within 24 hours of discovery or notification of the event (ie, before additional etiologic investigations have been concluded)
- The appropriate CRF (eg, Adverse Event CRF) that captures information necessary to facilitate the evaluation of treatment-emergent liver abnormalities is to be completed and sent to the Amgen.

Other events of hepatotoxicity and potential DILI are to be reported as serious adverse events if they meet the criteria for a serious adverse event defined in Section 9.2.2.

Additional Clinical Assessments and Observation

All subjects in whom investigational product(s) or protocol-required therapies is/are withheld (either permanently or conditionally) due to potential DILI as specified in Sections 6.5.1 and 6.5.2 or who experience AST or ALT elevations >3 x ULN are to undergo a period of "close observation" until abnormalities return to normal or to the subject's baseline levels. Assessments that are to be performed during this period include:

- Repeat AST, ALT, ALP, bilirubin (total and direct), and INR within 24 hours
- In cases of TBL > 2x ULN or INR > 1.5, retesting of liver tests, BIL (total and direct), and INR is to be performed every 24 hours until laboratory abnormalities improve

Testing frequency of the above laboratory tests may decrease if the abnormalities stabilize or the investigational product(s) or protocol-required therapies has/have been discontinued AND the subject is asymptomatic

- Initiate investigation of alternative causes for elevated AST or ALT and/or elevated TBL:
 - Obtain complete blood count (CBC) with differential to assess for eosinophilia
 - Obtain serum total immunoglobulin IgG, Anti-nuclear antibody (ANA), Anti Smooth Muscle Antibody, and Liver Kidney Microsomal antibody 1 (LKM1) to assess for autoimmune hepatitis

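### Protocol 6.5.2 limits its conditional withholding rules by eligibility criteria this trial does not have, so on the text some eligible subjects fall outside them

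*Protocol*

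**What the plan says.** Section 6.5.2 governs temporary withholding for possible liver injury. Its opening sentence names two groups. The first is subjects who do not meet the permanent-discontinuation criteria and have no underlying liver disease; the sentence then continues with "eligibility criteria requiring normal transaminases and TBL at baseline or subjects with underlying liver disease and baseline abnormal transaminases", which also supplies the second group. Five triggers follow:

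- AST or ALT > 8 x ULN
- AST or ALT > 5 x but < 8 x ULN for at least 2 weeks
- AST or ALT > 3 x ULN with signs or symptoms of hepatitis
- TBL > 3 x ULN
- ALP > 8 x ULN

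The action is the same for both groups: "Both atorvastatin and investigational product should be withheld pending investigation into alternative causes of DILI".

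The only hepatic laboratory criterion for entry is exclusion 213 in Section 4.1.2: "Persistent active liver disease or hepatic dysfunction, defined as aspartate aminotransferase (AST) or alanine aminotransferase (ALT) > 2 times the ULN", judged at screening or the lipid stabilization assessments. The Table 2 footnote and Section 7.2.1.2 repeat the 2 x ULN limit. No criterion in 4.1.1 or 4.1.2 mentions bilirubin.

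**The concern.** The first group is defined by a requirement this trial does not impose. The sentence looks like template text that was not adapted to the trial. It matters because it sets who is covered by a safety rule. A site following the words could conclude that the triggers do not apply to an eligible subject with, for example, a baseline ALT of 1.5 x ULN, or to an HCV-positive subject with normal transaminases.

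Such subjects are foreseeable. Exclusion 213 admits the first. HCV positivity is not a listed exclusion, and Table 1 schedules viral load in HCV-positive subjects on day 1 and at weeks 2, 8 and 12.

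What is at stake is whether withholding is required for these subjects or left to judgment. No efficacy result depends on it.

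**Working it through.** **Step 1: who is covered.** Cross the three baseline features the clause uses: underlying liver disease (yes/no), transaminases (normal, or above 1 and up to 2 x ULN) and TBL (normal/raised). This gives 2 x 2 x 2 = 8 states, none barred by exclusion 213. The wording allows two readings. On the strict reading the criteria do not exist, so the first group is empty. On the lenient reading the first group means subjects whose baseline values are in fact normal.

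| Liver disease | AST/ALT | TBL | Strict | Lenient | All-subjects wording |
|---|---|---|---|---|---|
| No | normal | normal | out | in | in |
| No | normal | raised | out | out | in |
| No | > 1 to 2 x ULN | normal | out | out | in |
| No | > 1 to 2 x ULN | raised | out | out | in |
| Yes | normal | normal | out | out | in |
| Yes | normal | raised | out | out | in |
| Yes | > 1 to 2 x ULN | normal | in | in | in |
| Yes | > 1 to 2 x ULN | raised | in | in | in |
| **Covered** | | | **2 of 8** | **3 of 8** | **8 of 8** |

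These count states, not patients. Five states are omitted under either reading; the strict reading adds a sixth, the subjects with no liver disease and entirely normal values.

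**Step 2: does another section fill the gap?**

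- *Section 6.5.1* has no such population clause, but it needs three things together: TBL > 2 x ULN or INR > 1.5; AST or ALT > 3 x ULN; and "no other cause for the combination of the above laboratory abnormalities is immediately apparent". An isolated rise does not qualify. Viral hepatitis, fatty liver disease and Gilbert's syndrome are among its listed alternative causes, so a subject with known liver disease may fail 6.5.1 because of that disease.
- *Appendix A* covers subjects already withheld under 6.5.1 or 6.5.2, or those "who experience AST or ALT elevations >3 x ULN are to undergo a period of" close observation. It requires monitoring and work-up; it does not order withholding. An isolated TBL > 3 x or ALP > 8 x ULN in an omitted subject triggers neither withholding nor close observation.
- *Section 8.2* is permissive: "The investigator and/or sponsor can decide to withdraw a subject(s) from investigational product and/or other protocol-required therapies".

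**Step 3: how much dosing could be affected.** Inputs are Table 1 and the Synopsis.

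- Q2W doses: day 1 and weeks 2, 4, 6, 8, 10 = 6.
- QM doses: day 1 and weeks 4, 8 = 3. "Final administration of IP (evolocumab or placebo) is at week 8 for QM treatment and week 10 for Q2W treatment".
- The Table 1 row "Chemistry, including fasting glucose" is marked at screening, end of lipid stabilization, day 1, week 8 and week 12. The day 1 sample is pre-dose, so on-treatment tests are at weeks 8 and 12 only.
- Week 8 result returned after the visit: Q2W, week 10 only = 1 of 6; QM = 0 of 3.
- Week 8 result available before the week 8 dose: Q2W, weeks 8 and 10 = 2 of 6; QM, week 8 = 1 of 3.
- On-study atorvastatin left after week 8: 12 - 8 = 4 of 12 weeks.
- Week 12 result: no doses remain.

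**The case against.** The strongest reply is that the sentence is garbled and its intent is plain. No subject can have eligibility criteria, so there is no settled literal reading. The introduction to 6.5 speaks of subjects with abnormal hepatic values without a baseline limit, and both named groups get identical thresholds. Nothing suggests that a middle group was deliberately left out. This stands as evidence of intent. It does not rescue the text: the introduction sends the reader to the criteria below it, and if everyone was meant, the clause can only exclude.

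The second reply is that there are more fallbacks than Section 8.2:

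- 6.2.1.2: IP stops if the investigator judges it not tolerated.
- 6.2.2.2: the medical monitor is contacted about atorvastatin intolerance.
- 8.3.2: a safety concern is a ground for removal from treatment.
- 9.1.1: clinical judgment decides removal for an adverse event.
- 9.2.1: laboratory results are reviewed for clinically significant change.
- Appendix A: for AST/ALT > 3 x ULN, repeat tests within 24 hours, a work-up for other causes and a hepatology consult.

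These make harm less likely, and for transaminase rises the practical gap is narrow. All except Appendix A depend on judgment, however, and none sets a threshold at which withholding is required. The gap is clearest for isolated TBL or ALP.

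Third, exclusions 201 and 215 and the final criterion on other significant disorders will remove some of these subjects. That also stands, but none of the three requires normal transaminases or TBL.

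**Conclusion.** The concern holds as a wording defect in a safety rule. Under either reading, Section 6.5.2 leaves eligible subjects outside its withholding triggers, and no other section makes withholding mandatory for them at those values.

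Its size is small. The documents give no prevalence for the omitted states, so no number of subjects is claimed; it is likely low on the lenient reading. The dosing limits above depend on laboratory turnaround, which is not stated. They cover scheduled tests only; an unscheduled test prompted by symptoms could trigger the rules earlier. Sample size, power, alpha, enrolment and all planned analyses are unaffected. It is worth correcting, at low priority.

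**What to change.** Replace the population clause in 6.5.2 so that it reads, in substance: for all subjects who do not meet the permanent-discontinuation criteria of Section 6.5.1, the withholding rules below apply to IP and the other protocol-required therapies. Leave all five triggers and the rechallenge provision as they are.

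The cost is one clause in an amendment. Section 12.1 requires investigator agreement and IRB/IEC approval, and Section 3.2 plans about 100 sites, so bundle the change with the next amendment. The documents show none after Amendment 3, and a standalone amendment for this alone would be hard to justify. No procedure, threshold or analysis changes.
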